### **People living with HIV**

PLWH are a major focus of this study, given the current significant evidence gap regarding what COVID-19 vaccine regimens would best benefit this group. PLWH will constitute the largest proportion of the study population, and study sites will be selected based on the presence of well-established systems for the diagnosis and care of PLWH.

Studies have consistently suggested that PLWH are at elevated risk of poor outcomes from COVID-19 compared to HIV-uninfected individuals. In a multicenter registry of 286 PLWH who got COVID-19, 94 percent were on HIV antiretroviral therapy and 57 percent were hospitalized, of which 16 percent were in the ICU with a 9 percent mortality rate. This study found that severe COVID-19 outcomes were associated with older age, lung disease, hypertension, and overall comorbidity burden (141). In the UK, a study of 123 PLWH out of 47,000 individuals hospitalized with COVID-19 found that the overall mortality was similar (27 percent for PLWH and 32 percent for people without HIV) but the adjusted hazard ratio was slightly higher for PLWH (1.52 vs 1.92) (142). A study of 50,167 people with COVID-19, of which 404 were PLWH, showed that the latter were more likely to have comorbidities that have risk factors for severe COVID-19, such as hypertension, diabetes, chronic kidney disease, and nicotine dependence (143). The degree of immunosuppression may play an important role in poor outcomes.

In addition to the elevated risk of morbidity and mortality from COVID-19, PLWH also face a risk of prolonged infections and the potential for a longer period of infectiousness and the development of new mutations. A growing number of studies involving people with immunocompromising conditions have demonstrated many instances of long-term viral shedding, sometimes infectious (41-43). In addition, an increasing number of studies suggest that prolonged infections in immunocompromised individuals, including PLWH, may be a major source of the multistep mutational changes associated with the emergence of VOCs (44-46). The evolution of new mutations enabling increased immunologic escape during chronic SARS-CoV-2 infection has been well-documented in PLWH (45).

To date, COVID-19 vaccine efficacy trials have generally only included a small number of PLWH, most of whom were required to have well-controlled disease, and very few studies have reported the number of endpoints in this population (12, 13). None of the primary vaccine efficacy trials enrolled adequate numbers of PLWH to determine vaccine efficacy in this population. Although there continues to be a lack of efficacy and safety data from controlled clinical trials on mRNA vaccines in PLWH, an increasing number of observational studies of PLWH suggest acceptable immunogenicity and safety (22, 24, 118, 119) .

In the case of a new HIV diagnosis, participants will be referred for HIV standard of care according to local guidelines. Participants with newly diagnosed HIV infection will have a CD4 and viral load assessment. If a participant is diagnosed with HIV infection at screening and antiretroviral treatment is initiated, the study vaccines may be administered approximately 2-4 weeks later to avoid overlapping AEs. In addition, the study team will support sites in monitoring for PLWH participating in the study with unsuppressed viral loads so that they can be referred to local resources in case they need adjustment of their ART regimen or interventions to support adherence.

Monitoring of the trial will include safety and efficacy monitoring of symptomatic cases of COVID-19. All confirmed cases of COVID-19 that develop during the study will receive special attention and close follow-up to permit early intervention to prevent complications, morbidity, and mortality. These include temperature monitoring, routine pulse oximetry, provision of oxygen, steroids and other medications, and hospitalization.

### 3 Objectives and endpoints

All symptomatic COVID-19 endpoints will be evaluated using two case definitions, one used in the COVE study (8, 12) and the other using a case definition based on criteria from the CDC (144, 145). The first two primary objectives count COVID-19 and severe COVID-19 endpoints starting 14 days after the last pre-Month 6 dose until the Month 6 dose in the pre-Month 6 stage, and compare the rate of these endpoints between adult PLWH with vaccine-only immunity vs. adult PLWH with hybrid immunity. The third and fourth primary objectives count COVID-19 and severe COVID-19 endpoints starting 14 days after dose 3 until the end of follow-up in the post-Month 6 stage, and compare the rate of these endpoints in adult PLWH who were randomized and received mRNA-1273 vs. mRNA-1273.222 vaccine. Secondary objective 1 compares rates of COVID-19 and severe COVID-19 in the pre-Month 6 stage during a different period of follow-up: starting 14 days after dose 2 for participants who are SARS-CoV-2 negative at baseline and starting 14 days after dose 1 for participants who are SARS-CoV-2 positive at baseline. Answers to primary objectives 1 and 2 will be available earlier than answers to primary objectives 3 and 4, such that essentially, the trial has two stages answering study questions comparing hybrid vs. vaccine-only immunity, and comparing two different month 6 vaccinations.

Primary Objectives	Primary Endpoints
1. PRE-MONTH 6 STAGE : to assess the relative risk of symptomatic COVID-19 in Group 1 (PLWH who are SARS-CoV-2 negative at baseline) who receive a 2-dose mRNA-1273 vaccine regimen vs. in Group 2 (PLWH who are SARS-CoV-2 positive at baseline) who receive a 1-dose mRNA-1273 regimen, counting endpoints starting 1 day after Month 0 dose until Month 6 dose.	1. COVID-19: Positive result of acute SARS-CoV-2 infection as assessed by nucleic acid amplification testing (NAAT) of a nasal swab and the presence of a prespecified symptom or symptoms (see footnotes 2 and 3)
2. PRE-MONTH 6 STAGE : to assess the relative risk of severe COVID-19 in Group 1 (PLWH who are SARS-CoV-2 negative at baseline) who receive a 2-dose mRNA-1273 vaccine regimen vs. in Group 2 (PLWH who are SARS-CoV-2 positive at baseline) who receive a 1-dose mRNA-1273 regimen, counting endpoints starting 1 day after Month 0 dose until Month 6 dose.	2. Severe COVID-19: COVID-19 that meets the criteria listed in footnote 4
3. POST-MONTH 6 STAGE : to assess the relative risk of symptomatic COVID-19 after the Month 6 dose among those who received mRNA-1273 at Month 6 vs. those who received mRNA-1273.222 at Month 6, counting endpoints at least 14 days after the Month 6 dose until end of follow up.	3. COVID-19: same as above
4. POST-MONTH 6 STAGE : to assess the relative risk of severe COVID-19 after the Month 6 dose among those who received mRNA-1273 at Month 6 vs. those who received mRNA-1273.222 at Month 6, counting endpoints at least 14 days after the Month 6 dose until end of follow up.	4. Severe COVID-19: same as above

Primary Objectives	Primary Endpoints
5. To assess the safety and tolerability of mRNA-1273 and mRNA-1273.222 in adults who are at risk of severe COVID-19 in both the pre-Month 6 and post-Month 6 stages.	5. Adverse events: Solicited and unsolicited AEs collected for a subset of study participants. Serious adverse events (SAEs), adverse events of special interest (AESIs), collected for all participants throughout the study

 HIV-infection status and SARS-CoV-2 status are confirmed for each participant based on testing of samples collected during screening (serology) and at enrollment (NAAT). SARS-CoV-2 negative indicates both NAAT negative and serology negative.

 To be considered as a case of COVID-19 using the COVE case definition for the evaluation of the Primary Efficacy Endpoint, the following criteria must be met:

1. The participant must have experienced at least TWO of the following systemic symptoms: Fever ( $\geq 38^{\circ}\text{C}$ ), chills, myalgia, headache, sore throat, new loss of taste or smell, OR
2. The participant must have experienced at least ONE of the following respiratory signs/symptoms: cough, shortness of breath or difficulty breathing, OR clinical or radiographical evidence of pneumonia; AND
3. The participant must have at least 1 nasal swab (or respiratory sample, if hospitalized) positive for SARS-CoV-2 by NAAT within 14 days following the above systemic or respiratory symptoms.

 To be considered as a case of COVID-19 using the CDC-derived case definition for the evaluation of the Primary Efficacy Endpoint, the following criteria must be met:

1. The participant must have experienced at least ONE of the following systemic symptoms: Fever ( $\geq 38^{\circ}\text{C}$ ), chills, myalgia, headache, sore throat, new loss of taste or smell, OR
2. The participant must have experienced at least ONE of the following respiratory signs/symptoms: cough, shortness of breath or difficulty breathing, OR clinical or radiographical evidence of pneumonia; AND
3. The participant must have at least 1 nasal swab (or respiratory sample, if hospitalized) positive for SARS-CoV-2 by NAAT within 14 days of any of the above systemic or respiratory symptoms.

 To be considered as a case of severe COVID-19 for the evaluation of the Secondary Efficacy Endpoint, the following criteria must be met:

- A confirmed case of COVID-19, per a Primary Efficacy Endpoint case definition, plus any of the following:
  - Clinical signs indicative of severe systemic illness, Respiratory Rate  $\geq 30$  per minute, Heart Rate  $\geq 125$  beats per minute, SpO2  $\leq 93\%$  on room air at sea level or PaO2/FIO2  $< 300$  mm Hg, OR
  - Respiratory failure or Acute Respiratory Distress Syndrome (ARDS), (defined as needing high-flow oxygen, noninvasive or mechanical ventilation, or ECMO), evidence of shock (systolic blood pressure  $< 90$  mmHg, diastolic BP  $< 60$  mmHg or requiring vasopressors), OR
  - Significant acute renal, hepatic, or neurologic dysfunction, OR
  - Admission to an intensive care unit or death.

Secondary Objectives	Secondary Endpoints
1. PRE-MONTH 6 STAGE: to assess the relative risk of symptomatic COVID-19 and of severe COVID-19 in Group 1 (PLWH who are SARS-CoV-2 negative at baseline) vs. in Group 2 (PLWH who are SARS-CoV-2 positive at baseline), counting endpoints at least 14 days after the last pre-Month 6 dose (i.e., dose 2 for Group 1 and dose 1 for Group 2) until the Month 6 dose.	COVID-19 and severe COVID-19 as defined for the primary endpoints
2. PRE-MONTH 6 STAGE: to assess the relative risk of symptomatic COVID-19 and of severe COVID-19 in Groups 1 and 3 together (participants who are SARS-CoV-2 negative at baseline regardless of HIV status) vs. in Groups 2 and 4 together (participants who are SARS-CoV-	COVID-19 and severe COVID-19 as defined for the primary endpoints

Secondary Objectives	Secondary Endpoints
2 positive at baseline regardless of HIV status), counting endpoints starting 1 day after dose 1, and counting endpoints at least 14 days after the last pre-Month 6 dose (ie,, dose 2 for Group 1 and dose 1 for Group 2) until the Month 6 dose.	
3. POST-MONTH 6 STAGE : to assess the relative risk of symptomatic COVID-19 and of severe COVID-19 after the Month 6 dose in Group 1 (PLWH who are SARS-CoV-2 negative at baseline) and Group 2 (PLWH who are SARS-CoV-2 positive at baseline), separately and combined, among those who received mRNA-1273 at Month 6 vs. those who received mRNA-1273.222 at Month 6, counting endpoints at least 14 days after the Month 6 dose until end of follow up.	COVID-19 and severe COVID-19 as defined for the primary endpoints
4. POST-MONTH 6 STAGE : to assess the relative risk of virologically confirmed symptomatic COVID-19 and of severe COVID-19 after the Month 6 dose in Groups 1 and 3 together (participants who are SARS-CoV-2 negative at baseline regardless of HIV status) and in Groups 2 and 4 together (participants who are SARS-CoV-2 positive at baseline regardless of HIV status), respectively, among those who received mRNA-1273 at Month 6 vs. those who received mRNA-1273.222 at Month 6, counting endpoints at least 14 days after Month 6 dose until the end of follow up.	COVID-19 and severe COVID-19 as defined for the primary endpoints
5. PRE-MONTH 6 & POST-MONTH 6 STAGES : to assess the relative risk of symptomatic COVID-19 and of severe COVID-19 after the Month 6 dose by neutralization phenotype and Spike sequence features of acquired SARS-CoV-2 viruses (sieve analysis) in Groups 1 and 3 together (participants who are SARS-CoV-2 negative at baseline regardless of HIV status) and in Groups 2 and 4 together (participants who are SARS-CoV-2 positive at baseline regardless of HIV status), respectively, among those who received mRNA-1273 at Month 6 vs. those who received mRNA-1273.222 at Month 6, counting endpoints starting 1 day after dose 1, 14 days after the last pre-Month6 dose , or 14 days after Month 6 dose until the end of follow up.	COVID-19 and severe COVID-19 as defined for the primary endpoints; neutralization phenotypes and viral genotypic characteristics of SARS-CoV-2 at diagnosis.
6. PRE-MONTH 6 & POST-MONTH 6 STAGES : to assess the relative risk of SARS-CoV-2 infection defined by nucleocapsid protein seroconversion regardless of symptomology after the Month 6 dose in Group 1 (PLWH who are SARS-CoV-2 negative at baseline) and in Group 3 (people HIV-negative who are SARS-CoV-2 negative at baseline) combined, among those who received mRNA-1273 at Month 6 vs. those who received mRNA-1273.222 at Month 6, counting endpoints starting 1 day after dose 1, 14 days after the last pre-Month 6 dose , or 14 days after Month 6 dose until the end of follow up.	SARS-CoV-2 infection diagnosed by seroconversion throughout the study.

Secondary Objectives	Secondary Endpoints
7. PRE-MONTH 6 & POST-MONTH 6 STAGES: to assess the relative risk of asymptomatic SARS-CoV-2 infection defined by nucleocapsid protein seroconversion after the Month 6 dose in Group 1 (PLWH who are SARS-CoV-2 negative at baseline) and in Group 3 (people HIV-negative who are SARS-CoV-2 negative at baseline) combined, among those who received mRNA-1273 at Month 6 vs. those who received mRNA-1273.222 at Month 6, counting endpoints starting 1 day after dose 1, 14 days after the last dose before Month 6 dose, or 14 days after Month 6 dose until the end of follow up.	SARS-CoV-2 infection diagnosed by seroconversion in the absence of symptoms.
8. PRE-MONTH 6 & POST-MONTH 6 STAGES: to assess the relative risk of symptomatic COVID-19, and severe COVID-19 after the Month 6 dose in Groups 1 and 3 together (participants who are SARS-CoV-2 negative at baseline regardless of HIV status) and in Groups 2 and 4 together (participants who are SARS-CoV-2 positive at baseline regardless of HIV status), respectively, among those who received mRNA-1273 at Month 6 vs. those who received mRNA-1273.222 at Month 6, counting endpoints starting 1 day after dose 1 or 14 days after the last dose before Month 6 dose until the end of follow up.	COVID-19 and severe COVID-19 as defined above
9. To assess post-vaccination immune response markers and immune markers as correlates of risk of COVID-19 and as correlates of protection against COVID-19 in all study groups together.	SARS-CoV-2-specific neutralization antibody, binding antibody and cellular immune responses
10. To assess SARS-CoV-2 viral persistence and evolution among participants virologically diagnosed of SARS-CoV-2 infection in all study groups together.	SARS-CoV-2 viral load (as inferred from RT-PCR cycle threshold values) and viral whole genome sequences

Exploratory Objectives	Exploratory Endpoints
1. To assess the relative risk of COVID-19 and severe COVID-19 by baseline HIV infection status in participants.	COVID-19 and severe COVID-19 as defined for the primary endpoints
2. To estimate VE of COVID-19 and severe COVID-19 using counterfactual placebo	COVID-19 and severe COVID-19 as defined for the primary endpoints
3. Assess post-infection T-cell responses in participants who develop COVID-19	SARS-CoV-2-specific T-cell immune responses; COVID-19 as defined above
Additional Exploratory Objectives	
4. To further evaluate immunogenicity of the vaccine, additional assays may be performed	
5. To conduct analyses related to furthering the understanding of SARS-CoV-2, coronavirus, immunology, vaccines, and clinical trial conduct	

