#### 6.4.3 Analysis of relative risk between treatment arms

For the assessment of the coprimary efficacy objectives, this study uses two approaches for determining symptomatic COVID-19 cases, as previously defined in Section 3. For survival data analyses, the time of all participant-level failure and censoring events are reported relative to the time of enrollment (ie, first vaccination) for the pre-Month 6 stage objectives, and relative to the time of Month 6 dose for post-Month 6 stage. For the COVE-based endpoint definition, the time of diagnosis of COVID-19 and severe COVID-19 will be determined by the EAC adjudicators. For the CDC criteria-based definition, the time of diagnosis of lab-confirmed clinical COVID-19 is defined as the minimum date of reported qualifying COVID-19 symptoms and collection date of SARS-CoV-2 positive result (both must occur), and the time of diagnosis of severe COVID-19 to be the minimum date of reported qualifying severe COVID-19 symptoms and collection date of SARS-CoV-2 positive result (both must occur).

The time of diagnosis of the SARS-CoV-2 infection endpoint is the draw time of the first sample with a positive test result by either antibody seroconversion assays or by virus-detection via NAAT. The serology assays are used to ascertain infections occurred anytime during the study among baseline SARS-CoV-2 negative (NAAT and serology negative) participants to address Secondary objectives 1-8. The NAAT are used to ascertain recent or ongoing infections among both baseline SARS-CoV-2 negative and positive participants to address exploratory objectives. The time of diagnosis of the asymptomatic endpoint is the draw time of the first sample with a positive test result by virus detection assays or seroconversion with no reported COVID-19-like illness episodes between enrollment and 14 days after the timepoint at which SARS-CoV-2 infection is ascertained. In case of reinfection of SARS-CoV-2, the first occurrence of a given endpoint is considered.

In the primary and most secondary efficacy analyses, the failure times of participants never observed to be diagnosed with a given clinical endpoint will be right censored at the date of last contact at which endpoint status was assessed or study termination. Participants who report outside COVID-19 vaccines will be censored at the time of receiving such vaccination. Except where otherwise

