The relative risk (of COVID-19, severe COVID-19, SARS-CoV-2 infection, or SARS-CoV-2 asymptomatic infection) is defined as the incidence rate ratio between the 2 treatment groups in the pre-Month 6 stage or between the 2 treatment arms within a group in the post-Month 6 stage. When there are at least 7 severe COVID-19 endpoints at the primary analysis for a given relative risk assessment, both COVID-19 and severe COVID-19 are used as coprimary endpoints. Otherwise, severe COVID-19 is considered as a secondary endpoint. For the final analyses of the pre-Month 6 objectives, the incidence will be compared across groups by estimating the marginalized cumulative incidence of the endpoint overtime for each group, using a causal inference method that adjusts for potential confounders and accounts for right-censoring of failure times. Under causal assumptions, the marginalized cumulative incidence equals the causal cumulative incidence, interpreted as cumulative incidence if, hypothetically, the entire study population were assigned to the given group under consideration. Sensitivity analyses may also be conducted to account for unobserved confounding factors. For the final analyses of the post-Month 6 objectives, the RR between treatment arms within each group will also be estimated. The causal inference approach used for the pre-Month 6 stage analysis may also be applied for estimating the relative risk of each endpoint for the post-Month 6 dose objectives. More details will be described in the SAP. For analyses before the final analyses, the RR may be estimated from a Poisson regression analysis for both pre- and post-Month 6 stages. To assess potential time effects of vaccine efficacy, the Nelson-Aalen method will be used to plot the estimated cumulative incidence rates over time for the comparison groups. Additional analysis of RR by specified viral

strain categories may also be performed using competing risks failure time methods, as detailed in the SAP.

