### **8.1 Vaccine regimen**

#### **Groups 1 and 3 (SARS-CoV-2 negative at baseline)**

**Treatment 1 (for Groups 1A and 3A):** mRNA-1273 vaccine in 100 mcg dose to be administered as an IM injection into the deltoid muscle on Day 1, Day 29 and Day 169 (Months 0, 1, and 6)

**Treatment 2 (for Groups 1B and 3B):** mRNA-1273 vaccine in 100 mcg dose to be administered as an IM injection into the deltoid muscle on Day 1 and Day 29 (Months 0 and 1)

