#### **Groups 2 and 4 (SARS-CoV-2 positive at baseline)**

**Treatment 3 (for Groups 2A and 4A):** mRNA-1273 vaccine to be administered as an IM injection into the deltoid muscle on Day 1 and Day 169 (Months 0 and 6)

**Treatment 4 (for Groups 2B and 4B):** mRNA-1273 vaccine to be administered as an IM injection into the deltoid muscle on Day 1 (Month 0)

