## Appendix K Visit windows

### Groups 1 and 3

Visit Number	Visit Type	Lower Allowable Window	Lower Target Window	Target Day 	Upper Target Window	Upper Allowable Window
01	Screening	-56	-		-	0
02	Vaccination 1	-	-0	1	+0	0
03	Vaccination 2		-3	29	+7	+14
04	Follow-up 		-3	57	+7	+14
05	Vaccination 3	-28	-7	169	+14	+28
106	Follow-up 		-7	197	+7	+16
107	Follow-up 	-17	-7	231	+7	+16
108	Follow-up 	-17	-7	265	+7	+16
109	Follow-up 	-17	-7	299	+7	+16
110	Follow-up 	-17	-7	333	+7	+16
111	Follow-up 	-15	-7	365	+7	+15
112	Follow-up 	-15	-7	396	+7	+14
113	Follow-up 	-15	-7	426	+7	+14
114	Follow-up 	-15	-7	456	+7	+14
115	Follow-up 	-15	-7	486	+7	+14
116	Follow-up 	-15	-7	516	+7	+14
117	Follow-up 	-16	-7	547	+7	+14

1. Target dates are relative to Visit 2 (Enrollment/Randomization), except for cases described in footnote 2.

2. Target dates are relative to the vaccination visit before.

## Groups 2 and 4

Visit Number	Visit Type	Lower Allowable Window	Lower Target Window	Target Day 	Upper Target Window	Upper Allowable Window
01	Screening	-56	-		-	0
02	Vaccination 1	-	-0	1	+0	0
03	Follow-up		-3	29	+7	+14
04 						
05	Vaccination 2	-28	-7	169	+14	+28
106	Follow-up 		-7	197	+7	+16
107	Follow-up 	-17	-7	231	+7	+16
108	Follow-up 	-17	-7	265	+7	+16
109	Follow-up 	-17	-7	299	+7	+16
110	Follow-up 	-17	-7	333	+7	+16
111	Follow-up 	-15	-7	365	+7	+15
112	Follow-up 	-15	-7	396	+7	+14
113	Follow-up 	-15	-7	426	+7	+14
114	Follow-up 	-15	-7	456	+7	+14
115	Follow-up 	-15	-7	486	+7	+14
116	Follow-up 	-15	-7	516	+7	+14
117	Follow-up 	-16	-7	547	+7	+14

1. Target dates are relative to Visit 2 (Enrollment/Randomization), except for cases described in footnote 2.

2. Target dates are relative to the vaccination visit before.

3. Grayed out Visit 4 does not apply for these groups.

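### The 14-days-after-last-dose window in secondary objectives 1 and 2 gives the two-dose groups 126 days and the one-dose groups 154, so a cumulative incidence ratio would read about 0.82 at equal constant risk

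*Protocol*

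**What the plan says.** Secondary objective 1 compares Group 1 with Group 2, "counting endpoints at least 14 days after the last pre-Month 6 dose (i.e., dose 2 for Group 1 and dose 1 for Group 2". Counting in both groups ends when the Month 6 vaccination is given. Secondary objective 2 compares Groups 1 and 3 with Groups 2 and 4 over two windows: "counting endpoints starting 1 day after dose 1, and counting endpoints at least 14 days after the last pre-Month 6 dose". The first of these is the same for everyone; the second is not.

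Protocol Section 8.1 schedules mRNA-1273 in Groups 1A and 3A "on Day 1, Day 29 and Day 169 (Months 0, 1, and 6" and in Groups 2A and 4A "on Day 1 and Day 169 (Months 0 and 6". The B arms differ only in the Month 6 product. In Appendix K, "Target dates are relative to Visit 2 (Enrollment/Randomization), except for cases described in footnote 2"; footnote 2 does not apply to the vaccination visits, so a late dose 2 does not move the Month 6 target.

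Protocol Section 6.4.3 says failure and censoring times "are reported relative to the time of enrollment (ie, first vaccination) for the pre-Month 6 stage objectives". It excludes participants who had the endpoint before counting starts. For the final pre-Month 6 analyses, "the incidence will be compared across groups by estimating the marginalized cumulative incidence of the endpoint overtime for each group". Section 6.3.1 likewise speaks of cumulative incidence ratios.

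Other text points to rates. Section 6.4.3 says the relative risk "is defined as the incidence rate ratio between the 2 treatment groups in the pre-Month 6 stage" and allows Poisson regression before the final analyses. The introduction to Section 3 says that secondary objective 1 compares rates.

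**The concern.** Cumulative incidence grows with the length of the window. Followed as written, the final-analysis text gives the one-dose groups 28 more days in which to accumulate cases (154/126 = 1.22, or 22% more). The vaccine-only versus hybrid ratio is then pulled down by the calendar and not by protection. The extra days are also the earliest ones: a case on Day 30 is an event in Group 2 but removes the participant from the analysis in Group 1. Confounder adjustment cannot repair this, because window length is fixed by group.

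Hybrid versus vaccine-only immunity is the main pre-Month 6 question. A smaller ratio in this window than in the primary window could be taken to mean that the hybrid advantage shrinks once the two-dose series is complete.

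**Working it through.** **Inputs.** Dose days 1, 29 and 169 (Protocol Section 8.1). Visit windows from Appendix K: dose 2 at Day 29, target -3/+7, upper allowable +14; Month 6 dose at Day 169, allowable -28/+28. Group sizes 4,200 and 8,400 and a 5% six-month background incidence (Section 6.3.1). Interim annual incidence in PLWH of 7.1% and 2.2% (Section 2.1).

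**1. The plan's nearest figure.** Table 6-2, VE 60% and RR 2.0, states 167 events and 99% power for the common Month 0-6 window. With p1 = 0.05 x 0.40 = 0.020 and p2 = 0.010, expected events are 4,200 x 0.020 + 8,400 x 0.010 = 168 (163.8 after 2.5% six-month dropout), and an exact conditional binomial test gives power 0.990. This row reproduces. The documents give no expected events, power or ratio for the 14-day window.

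**2. Window lengths on target days.**
- Two-dose groups: start 29 + 14 = Day 43; 169 - 43 = 126 days.
- One-dose groups: start 1 + 14 = Day 15; 169 - 15 = 154 days.

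**3. Cumulative incidence ratio at equal constant hazard r.** Ratio = [1 - exp(-126r/365.25)] / [1 - exp(-154r/365.25)]. For small r this is 126/154 = 0.818. At 2.2% to 10% per year it is 0.819 to 0.821.

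**4. Visit timing, one visit moved at a time.**

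| Change | Days | Ratio |
|---|---|---|
| Dose 2 on Day 26 | 129/154 | 0.84 |
| Dose 2 on Day 36 | 119/154 | 0.77 |
| Dose 2 on Day 43 | 112/154 | 0.73 |
| Month 6 dose on Day 141 | 98/126 | 0.78 |
| Month 6 dose on Day 197 | 154/182 | 0.85 |

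With dose 2 on Day 43 and the Month 6 dose on Day 141 together, it is 84/126 = 0.67. Every case is below 1.

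**5. Interim rates.** The rate ratio is 7.1/2.2 = 3.23. Over the unequal windows, cumulative incidence is 2.42% against 0.92%, a ratio of 2.62. Over a common 126 days the ratio is 3.20.

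**6. Incidence rate ratio instead.** Let both groups share the same hazard, f times as high in Days 15-43 as later. With person-time counted from each group's own start, the rate ratio is 154/(28f + 126) and the cumulative ratio is 126/(28f + 126).

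| f | Rate ratio | Cumulative ratio |
|---|---|---|
| 0.5 | 1.10 | 0.90 |
| 1 | 1.00 | 0.82 |
| 2 | 0.85 | 0.69 |

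**7. False rejection if counts are compared with no allowance for window length.** Take 4% per year in both groups (0.05 x 0.40 per six months, doubled). Expected events are 57.6 and 140.5, about 198 in all, and the exact two-sided 5% binomial test rejects true equality about 22% of the time. This uses the ceiling sample sizes and target-day visits, so it is illustrative only.

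**The case against.** The strongest reply is that the protocol defines relative risk as an incidence rate ratio and describes this very objective as a comparison of rates. A rate ratio with person-time from each group's own start is 1.00 at equal constant hazard. This stands as far as it goes: 0.82 is conditional on the measure. It does not dispose of the point. The sentence on the final analyses names cumulative incidence and leaves Poisson regression to earlier ones. Step 6 shows that the rate ratio is neutral only under a constant hazard, whereas SAP Section 10.3 describes unpredictable change in the epidemic over calendar time.

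Second, Section 6.4.3 defers detail to the SAP. The SAP supplied covers the Month 6 boost and refers to a separate pre-Month 6 SAP that is not among the documents. For the post-Month 6 stage, the supplied SAP ties the time origin to the start of counting and reads both arms at one t_0 (Sections 4 and 10.2). The same device would remove the window-length effect here. This too stands, but nothing supplied shows it applied to this window.

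Third, 14 days after completing each regimen is a recognisable target, and a common start gives up matching on time since last dose. That is a real trade-off. Table 6-1 also admits Group 2 members with one or two pre-Month 6 doses, so a uniform 154 days is an approximation.

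A reader might infer that the reported secondary result carries a 0.82 bias, that all of secondary objective 2 is affected, or that the hybrid advantage would vanish. The documents support none of these. The measure is not settled, objective 2 also has a common window, and at the interim rates the ratio stays well above 1.

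**Conclusion.** The unequal windows are certain: 126 against 154 days on target days, in secondary objective 1 and in the second window of secondary objective 2. Under the cumulative incidence comparison on the enrollment time scale that the final-analysis text describes, equal constant hazards give about 0.82, or 0.73 to 0.85 as one visit at a time moves. The interim rates would read as 2.6 instead of 3.2, with the direction unchanged. Under the rate ratio that the protocol also names, the ratio is 1.00 at constant hazard, and 1.10 or 0.85 if the early hazard is half or double the later one. These figures assume the same hazard by study day in both groups, except for the interim illustration, which uses each group's own constant rate.

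A reader might extend this to primary objectives 1 and 2. The objectives table and Section 6.4.3 do not support that: both count from 1 day after the first dose in every group. The introduction to Section 3, however, says the primary objectives count from 14 days after the last pre-Month 6 dose, and then calls the secondary window a different period. If that prose governed, the same imbalance would reach the primary comparison.

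**What to change.** For this window only, leave objective 2's common window from 1 day after dose 1 unchanged. Name one measure and compare the groups over equal follow-up, in one of two ways:

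- **Common start.** Count all groups from 14 days after the Month 1 visit (Day 29 + 14 = Day 43; use Day 43 if that visit was missed), among those under follow-up and endpoint-free at that point. Groups 2 and 4 already have a Day 29 follow-up visit, so no new data are needed.
- **Own start, common read-off.** Reset the time origin to each group's counting start and read both groups at the same t_0, as the supplied SAP does post-Month 6. On target days Group 1 supports t_0 up to 126 days. This keeps time since last dose matched, but the groups still cover different study days (43-169 against 15-141), so it does not remove the dependence on hazard shape.

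The common start costs Group 2 about 28 days of counting: 8,400 x 0.022 x 28/365 = 14 of about 78 expected cases, at 2.2% per year and the ceiling sample size. Time since last dose is then no longer matched, so the window as the protocol now defines it can be kept as a sensitivity analysis reported as a rate ratio, with person-time from each group's counting start.

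Also reconcile the introduction to Section 3 with the objectives table on the primary window, and confirm that the pre-Month 6 SAP uses the same rule.
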